6.12.4. Clinical Laboratory Evaluation

Clinical laboratory assessments include hematology, serum chemistry, urinalysis, and safety-related immune markers such as neutrophil counts.

Continuous laboratory tests will be summarized as changes from baseline to last observation for patients who have both baseline and at least 1 postbaseline result for Periods 2 and 3, respectively:

- The scheduled visits/measurements will be included. The unscheduled visits and the repeat measurements will be excluded.
- Both international system of unit (SI) and conventional unit will be summarized when different.
- For the Safety Population Period 2, the comparisons between and among treatment group will be conducted using an ANCOVA with treatment group and baseline value in the model.
- Data will be analyzed based on original scale.

Laboratory test observed values at each visit (starting at baseline) and change from baseline to each scheduled visit, respectively, will be displayed in box plots for patients who have both a baseline and at least 1 postbaseline result. These box plots will be used to evaluate trends over time and to assess a potential impact of outliers on central tendency summaries.

- The scheduled visits/measurements will be included. The unscheduled visits and the repeat measurements will be excluded.
- The displays with both SI and conventional units will be provided when different.
- The following summary statistics will be included as a table below the box plot: number of patients with a baseline and at least 1 postbaseline result, mean, SD, minimum, Q1, median, Q3, and maximum.
- Data will be summarized based on original scale.
- On the box plots of the laboratory test observed values, the lines of the reference ranges/limits (by using the performing laboratory reference ranges) will be added. In cases where limits vary across age and gender, the lowest of the high limits and the highest of the low limits will be used.

The number and percentage of patients with a treatment-emergent or follow-up emergent abnormal, high, or low for laboratory tests will be summarized by treatment group for each study period (Period 2, 3, and 4, respectively). The comparisons between and among treatment groups will be conducted using Fisher's exact test for the Safety Population for the Period 2.

- All scheduled, unscheduled, and repeated measurements will be included.
- Performing laboratory will be used to defined the low and high limits reference ranges except for leukocyte, neutrophil, lymphocyte, and platelet counts where Lilly defined LLN will be used for these 4 labs.

- Alanine aminotransferase (ALT), aspartate aminotransferase (AST), total bilirubin, alkaline phosphatase (ALP), neutrophils, leukocytes, platelets, and lymphocytes will not be included in the treatment-emergent abnormal, high, or low summary as a separate analysis addressing the risk of liver injury is described in Section 6.12.3.1 and a separate analysis addressing leukocytes (WBC) and platelets is described in Section 6.12.4.1. Note that the ranges are defined by a lower limit of normal (LLN) and an upper limit of normal (ULN). A result that is greater than or equal to the LLN and less than or equal to the ULN is considered to be within the normal ranges.
- For categorical laboratory tests:
 - Treatment-emergent abnormal value is defined as a change from normal at all baseline visits to abnormal at any time postbaseline during the treatment period.
 - Follow-up emergent abnormal result is defined as a change from normal at baseline to abnormal at any time during the follow-up period.
- For continuous laboratory tests:
 - Treatment-emergent high value is defined as a change from a value less than or equal to the ULN at all baseline visits to a value greater than the ULN at any time postbaseline during the treatment period.
 - Treatment-emergent low value is defined as a change from a value greater than or equal to the LLN at all baseline visits to a value less than the LLN at any time postbaseline during the treatment period.
 - Follow-up emergent high value is defined as a change from a value less than or equal to the ULN at baseline to a value greater than the ULN at any time postbaseline during the follow-up period.
 - Follow-up emergent low value is defined as a change from a value greater than or equal to the LLN at baseline to a value less than the LLN at any time postbaseline during the follow-up period.

By-patient listing of laboratory test values will be provided. Listing of laboratory tests reference ranges (Lilly defined LLN for leukocyte, neutrophil, lymphocyte and platelet counts, and Performing Lab reference ranges for other lab tests) will be provided. By-patient listing of abnormal laboratory test results (criteria defined in the shift tables excluding the normal category) for parameters of special interest (hepatic, leukocytes, and platelets) will be provided.

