## Schedule of Activities, Protocol I1F-MC-RHBW (Periods 1-2)

	Screening (Period 1)	Baseline Randomization	Blinded Treatment Dosing Period (Period 2) a					
CRF Visit (V) Number	V1	V2	V3	V4	V5	V6	V7	V8
Weeks Since Randomization		W0	W1	W2	W4	W8	W12	W16
Study Days	Up to -42 d	0	7 ± 2d	14 ± 2d	28 ± 2d	56 ± 4d	84 ± 4d	112 ± 4d
Laboratory Tests								
HLA-B27 n	X							
CRP	X o	X	X	X	X	X	X	X
Administer PPD/Collect QuantiFERON®- TB Gold/T-SPOT®P	X							
ECG	X							
FSH q	X							
HIV/HCV	X							
HBV	X r	X r					X r	
Serum pregnancy test s	X							
Urine pregnancy test s		X					X	
Serum chemistry	X	X			X	X	X	X
PTT, PT/INR	X							X
Lipid panel (fasting) t		X						X
Hematology	X	X			X	X	X	X
Urinalysis	X							X
TSH and free T4	X							
Non-pharmacogenetic biomarker exploratory storage samples (urine, serum, plasma, RNA, and whole blood) u		X	X v	X v	X	X v	X v	X
Pharmacogenetic exploratory sample (DNA) u,aa		X						
Immunogenicity testing w		X	X	X	X	X	X	X
PK sampling w,x		X	X	X	X	X	X	X

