### Clinical Safety Laboratory Tests to be Performed by Sponsor-Designated Laboratory

Hematologya:	Serum Chemistrya:
Hemoglobin	Sodium
Hematocrit	Potassium
Erythrocyte count (RBC)	Bicarbonate
Mean cell volume (MCV)	Chloride
Mean cell hemoglobin concentration (MCHC)	Phosphorus
Leukocytes (WBC)	Total bilirubin
Platelets	Direct bilirubin
Absolute counts of:	Alkaline phosphatase
Neutrophils, segmented	Alanine aminotransferase (ALT/SGPT)
Neutrophils, juvenile (bands)	Aspartate aminotransferase (AST/SGOT)
Lymphocytes	Blood urea nitrogen (BUN)
Monocytes	Uric acid
Eosinophils	Creatinine
Basophils	Calcium
Urinalysis (dipstick)a:	Glucose
Color	Albumin
Specific gravity	Cholesterol (total)
pH	Total protein
Protein	Calculated creatinine clearance b
Glucose	Creatine phosphokinase (CPK)
Ketones	Triglycerides
Bilirubin	Gamma-glutamyl transferase (GGT)
Urobilinogen	
Blood	Lipid Panelc:
Nitrite	Low density lipoprotein (LDL)
Urine creatinine	High density lipoprotein (HDL)
Leukocyte esterase	Very low density lipoprotein (VLDL)
Other Tests:	
Human immunodeficiency virus antibody (HIV) f	Pregnancy test (serum) d
Hepatitis B surface antigen (HBsAg) f	Follicle-stimulating hormone (FSH) e
Anti-hepatitis B surface antibody (HBsAb) f	Thyroid-stimulating hormone (TSH) and free T4
Anti-hepatitis B core antibody (HBcAb) f	Ixekizumab serum concentration (pharmacokinetic [PK])
Anti-hepatitis C antibody f,h	Partial thromboplastin time (PTT)
HBV DNA g	Prothrombin time/international normalized ratio (PT/INR)
High sensitivity C-reactive protein (hsCRP)	Exploratory storage samples (urine, serum, plasma, RNA, and whole blood)
Purified protein derivative (PPD) i	Pharmacogenetic sample (DNA)
Urine pregnancy test d (assayed by clinical study site)	Immunogenicity testing (anti-ixekizumab Ab)
QuantiFERON®-TB Gold test i	
T-SPOT® i	
HLA-B27	

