**Clinical Safety Laboratory Tests**

Abbreviations: Ab = antibody; DNA = deoxyribonucleic acid; HBV = hepatitis B virus; RNA = ribonucleic acid; RBC = red blood cells; SGOT = serum glutamic oxaloacetic transaminase; SGPT = serum glutamic pyruvic transaminase; T4 = thyroxine; WBC = white blood cells.

- a. Unscheduled blood chemistry, hematology, and urinalysis panels may be performed at the discretion of the investigator.
- b. Cockcroft-Gault calculation is used for the calculated creatinine clearance.
- c. For the fasting lipid profile, patients are not to eat or drink anything except water for 12 hours prior to test. Fasting is not required for the screening visit (Visit 1).
- d. Serum pregnancy test for all women <60 years of age who are still of childbearing potential at Visit 1 only and will be performed centrally; after Visit 1, urine pregnancy test performed locally for women of childbearing potential.
- e. Women  $\geq 40$  and <60 years of age who have had a cessation of menses for  $\geq 12$  months will have an FSH test confirming nonchildbearing potential ( $\geq 40$  mIU/mL).
- f. Test required at Visit 1 to determine eligibility of patient for the study.
- g. HBV DNA testing will be done in those patients who are HBcAb+ at screening.
- h. See exclusion criteria (Section 5.2) specific to Hepatitis C antibody. A confirmatory test for HCV will be performed if the patient is positive for HCV antibody.
- i. In countries where the QuantiFERON®-TB Gold test or T-SPOT® is available, either test may be used instead of the PPD TB test. The QuantiFERON®-TB Gold test may be performed locally or centrally; the T-SPOT® must be performed locally.

---

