6.1.2. General Considerations for Analyses during the Extended Treatment Period (Period 3)

Unless otherwise specified, Period 3 starts at the first injection of study treatment at Week 16 (Visit 8) and ends on the date of Week 52 (Visit 15) or the ETV (between Weeks 16 and 52).

For the efficacy and health outcomes analyses, baseline is defined as the last available value before the first injection in Period 2 and, in most cases, will be the value recorded at Week 0 (Visit 2).

Unless otherwise specified, for the safety analyses during Period 3, baseline is defined as the last available value before first injection of ixekizumab in Period 3. In most cases, this will be the measure recorded at Week 16 (Visit 8). For treatment-emergent adverse events (TEAEs), baseline is considered as those events that are ongoing before the first injection of the study treatment at Week 16.

The number and percentage of patients having a categorical efficacy response (for example, ASAS40) will be summarized by treatment group for all scheduled visits (nonresponder imputation [NRI]), including Week 52 (Visit 15) during Period 3.

In addition, the number and percentage of patients achieving response on ASAS20 for those patients who did not achieve it at Week 16, and the number and percentage of patients maintaining response for those who achieved response at Week 16 will be summarized by treatment group for all scheduled visits (NRI), including Week 52 (Visit 15) during Period 3. Similar summary will be provided for ASAS40.

Each continuous efficacy and health outcomes score and change from baseline (or percent improvement) will be summarized by treatment group at all scheduled visits, including Week 52 (Visit 15) using descriptive statistics (n, mean, SD, median, minimum, and maximum). Missing data will be imputed using mBOCF method (Section 6.3.2).

The categorical safety measures will be summarized with incidence rates. The mean change of the continuous safety measures will be summarized at all scheduled visits.

6.1.3. General Considerations for Analyses during Combined Blinded Treatment Dosing Period and Extended Treatment Period (Combined Periods 2 and 3)

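### SAP 6.12.4 mixes fasting-scheduled and other draws of triglycerides and glucose, which can distort the by-visit plots and inflate the uncontrolled Period 3 and Period 4 rates of high values

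*SAP*

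**What the plan says.** Protocol Appendix 3 puts glucose, total cholesterol and "Triglycerides" in the Serum Chemistry list. The Lipid Panel contains only LDL, HDL and VLDL, and its footnote reads: "For the fasting lipid profile, patients are not to eat or drink anything except water for 12 hours prior to test". The same footnote waives fasting at Visit 1. In the Schedule of Activities (Appendix 2) the fasting footnote sits on the lipid panel row. The row headed "Serum chemistry" carries no such footnote in any period.

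SAP 6.12.4 applies three summaries to continuous analytes:

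- change from baseline to last observation;
- box plots of the value at each visit and of the change to each scheduled visit, with the purpose "These box plots will be used to evaluate trends over time and to assess a potential impact of outliers on central tendency summaries";
- treatment-emergent and follow-up emergent high or low, using all scheduled, unscheduled and repeat measurements.

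On the last it says "Treatment-emergent high value is defined as a change from a value less than or equal to the ULN at all baseline visits", followed by a value above ULN at any time post-baseline in the period. Eight analytes are taken out of the treatment-emergent table because they are analysed elsewhere. Triglycerides and glucose are not among them.

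For Period 3 safety, SAP 6.1.2 says "baseline is defined as the last available value before first injection of ixekizumab in Period 3", which it expects to be Week 16 in most cases. For Period 4, SAP 6.1.4 uses the last non-missing assessment on or before Week 52 or the early termination visit (ETV).

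**The concern.** The schedule separates fasting-scheduled visits from the rest, and the analysis does not use that information. If triglycerides and glucose are higher when the patient has not fasted, two displays are affected.

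The box plots place draws of both kinds along one axis, so the medians can rise and fall with the visit schedule and look like a time trend.

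The treatment-emergent count asks whether any draw exceeds ULN after a baseline at or below it. In Period 3 the baseline is usually fasting-scheduled and most later draws are not. Period 3 has no control arm and no between-group comparison, so nothing cancels the shift. A reader of the 52-week table could take the excess for a metabolic effect of longer exposure, or could dismiss a real effect as food. Follow-up emergent highs in Period 4 raise the same issue for patients who complete Week 52.

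**Working it through.** **Step 1: schedule, from Appendix 2.**

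| Draw | Serum chemistry | Fasting lipid panel |
|---|---|---|
| Visit 1 | yes | no |
| Week 0 | yes | yes |
| Weeks 4, 8, 12 | yes | no |
| Week 16 | yes | yes |
| Week 20 | yes | no |
| Week 24 | yes | yes |
| Weeks 28, 32 | yes | no |
| Week 36 | yes | yes |
| Week 44 | yes | no |
| Week 52 | yes | yes |
| ETV, V801 to V803 | yes | no |

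Scheduled post-baseline chemistry draws with no fasting rule number 3 of 4 in Period 2 and 4 of 7 in Period 3, so (3 + 4)/(4 + 7) = 7/11 overall.

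**Step 2: baseline against follow-up, by period.**

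- Period 2 emergence: the baseline is all results from Visit 1 to first injection (SAP 6.1.1 and 6.12). It includes the non-fasting Visit 1 draw, which already screens out some patients whose values are high when not fasting.
- Period 3 emergence: the baseline is usually Week 16, fasting-scheduled. Weeks 20, 28, 32 and 44 are not.
- Period 4, Week 52 completers: the baseline is fasting-scheduled. V801 to V803 are not.
- Change to last observation: completers run from Week 0 to 16 and from Week 16 to 52, fasting-scheduled at both ends. A patient who stops before Week 16 ends on a draw with no fasting rule.

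**Step 3: size in Period 3 (illustration).** The documents give no rates of high values by fasting state, so there is no plan figure to reproduce and every input here is an assumption. Log triglyceride has total SD 0.5 and within-patient SD 0.22, so the between-patient SD is √(0.5² − 0.22²) = √0.2016 = 0.449. ULN is at the 84th percentile of fasting values, which is 0.5 above the fasting log mean. A non-fasting draw is multiplied by m, and the drug has no effect.

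Chance that a single draw is high: 1 − Φ((0.5 − ln m)/0.5).

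- Fasting: 1 − Φ(1) = 15.9%
- m = 1.1: 1 − Φ(0.809) = 20.9%
- m = 1.2: 1 − Φ(0.635) = 26.3%
- m = 1.3: 1 − Φ(0.475) = 31.7%

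The SAP rule was then simulated in 400,000 patients, with a fasting baseline at or below ULN and any of the seven Period 3 draws above it:

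| Rise when not fasting | As scheduled | All seven fasting |
|---|---|---|
| 10% | 27.5% | 22.1% |
| 20% | 33.8% | 22.1% |
| 30% | 40.7% | 22.1% |

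The excess is about 5, 12 and 19 percentage points.

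**Step 4: a second model.** This one assumes a per-visit chance above ULN of 0.10 fasting and 0.20 non-fasting, with within-patient correlation 0.7. Period 3 gives 33.9% as scheduled against 20.9% all fasting. Period 2 gives 21.1% against 12.4%, even with the Visit 1 screen. With 0.10 in both states nothing moves: 20.8% against 20.9% in Period 3, and 12.5% against 12.4% in Period 2.

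**Step 5: between-arm test in Period 2.** All arms follow one schedule, so with no drug effect they share one rate. The exact type I error of Fisher's test with 100 per arm is 0.029 at a common rate of 10% and 0.036 at 40%, below 0.05.

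**The case against.** The other side has several good points.

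- No passage sets a fasting rule for chemistry at any visit. That chemistry is fasting at Weeks 0, 16, 24, 36 and 52 is inferred from the shared visit. Appendix 3 waives fasting at Visit 1 although no lipid panel is scheduled there, which hints that the fast may have been meant more widely. Protocol 8.4.3 refers sites to a central laboratory manual that is not available here. This stands, and it is why the term used is fasting-scheduled rather than fasting.
- The food effect is assumed. A reader might infer that the rates must move by construction. They do not: with no food effect they stay put. Only triglycerides were modelled, so nothing is shown about the size for glucose.
- A reader might infer that the box plots pool visits. They are drawn visit by visit, and their weakness is mixed fasting state along one axis. Only the treatment-emergent and follow-up emergent counts combine draws.
- A reader might also infer that the Period 2 arm comparison is biased. The arms share one schedule and Visit 1 cushions emergence. A common shift can dilute the comparison or add noise, but does not create a false difference.
- Metabolic effects are not among the listed adverse events of special interest, and by-patient listings of laboratory values are already planned. That lowers the priority. It does not correct the summary tables that most readers will use.

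**Conclusion.** The point holds in limited form. The schedule and the SAP's silence on fasting are plain in the documents. The consequence is conditional: if non-fasting values run higher, the by-visit plots can saw-tooth, and absolute rates of highs are inflated in Period 3 and, for Week 52 completers, in Period 4. On the stated triglyceride assumptions, Period 3 shows about 28% to 41% instead of 22%. These figures illustrate direction and order of size; they are not estimates for this trial.

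The documents do not support a claim of biased efficacy or safety testing between arms. The one exception in Period 2 is change to last observation, where the fasting status of the final draw depends on dropout. That effect is confined to discontinuers, is expected to be small, and cannot be sized from the documents. This is a cheap improvement to safety reporting, not a flaw in the main analyses.

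**What to change.** In SAP 6.12.4:

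- Keep all draws. Flag each triglyceride and glucose result, and total cholesterol for consistency, as fasting-scheduled (Weeks 0, 16, 24, 36, 52) or not.
- Mark the flag on the box plots.
- Beside the all-visit table, present change from baseline and treatment-emergent or follow-up emergent highs separately for fasting-scheduled visits and for other visits.
- Note under the tables that the number of visits differs between the summaries, so their rates are not directly comparable.

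Restricting the tables to fasting-scheduled visits would be worse. The ETV has no lipid panel, so patients who stop before Week 16 would drop out of the Period 2 summaries, and those who stop before Week 24 out of Period 3. It would also cut the Period 3 looks from seven to three. In the Step 3 model that alone gives 14.6%, below the 22% all-fasting figure.

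The cost is SAP wording, a visit flag and a few extra table rows for two or three analytes. No new data are needed.

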### **9.5.2. Clinical Laboratory Tests**

Laboratory assessments will be presented as mean changes from baseline, and as incidence of treatment-emergent abnormal, high, or low laboratory values (see below). Shift tables will be presented for selected parameters.

- For categorical lab tests:
  - Treatment-emergent **abnormal** value = a change from normal at all baseline visits to abnormal at any time postbaseline.
- For continuous lab tests:
  - Treatment-emergent **high** value = a change from a value less than or equal to the high limit at all baseline visits to a value greater than the high limit at any time postbaseline.
  - Treatment-emergent **low** value = a change from a value greater than or equal to the low limit at all baseline visits to a value less than the low limit at any time postbaseline.

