6.12.4.1. Leukocytes (WBC) and Platelets

Further analyses will be conducted for total leukocytes, neutrophils, platelets, lymphocytes, monocytes, eosinophils, and basophils. Neutrophils will include both segmented neutrophils and absolute neutrophils (derived by adding segmented neutrophils and band neutrophil). The segmented neutrophils and absolute neutrophils will be summarized using the same categories.

Shift table will be produced showing the number and percentage of patients shifting from baseline to a minimum postbaseline result in each relevant category by treatment groups for study Period 2, Period 3, and Combined Periods 2 and 3, respectively:

- Scheduled visits, unscheduled visits, and repeat measurements will be included.
- Baseline is defined as the minimum result during the defined baseline period or baseline.
- Use the minimum nonmissing postbaseline value within each study period.
- The parameters and categories are:
 - Leukocytes: $\geq 1 \times \text{LLN}$ (Normal), $< \text{LLN}$ to $\geq 3.0 \times 10^9/\text{L}$ (Grade 1), $< 3.0 \times 10^9/\text{L}$ to $\geq 2.0 \times 10^9/\text{L}$ (Grade 2), $< 2.0 \times 10^9/\text{L}$ to $\geq 1.0 \times 10^9/\text{L}$ (Grade 3), and $< 1.0 \times 10^9/\text{L}$ (Grade 4).
 - Neutrophils: $\geq 1 \times \text{LLN}$ (Normal), $< \text{LLN}$ to $\geq 1.5 \times 10^9/\text{L}$ (Grade 1), $< 1.5 \times 10^9/\text{L}$ to $\geq 1.0 \times 10^9/\text{L}$ (Grade 2), $< 1.0 \times 10^9/\text{L}$ to $\geq 0.5 \times 10^9/\text{L}$ (Grade 3), and $< 0.5 \times 10^9/\text{L}$ (Grade 4).
 - Platelets: $\geq 1 \times \text{LLN}$ (Normal), $< \text{LLN}$ to $\geq 75.0 \times 10^9/\text{L}$ (Grade 1), $< 75.0 \times 10^9/\text{L}$ to $\geq 50.0 \times 10^9/\text{L}$ (Grade 2), $< 50.0 \times 10^9/\text{L}$ to $\geq 25.0 \times 10^9/\text{L}$ (Grade 3), and $< 25.0 \times 10^9/\text{L}$ (Grade 4).
 - Lymphocytes: $\geq 1 \times \text{LLN}$ (Normal), $< \text{LLN}$ to $\geq 0.8 \times 10^9/\text{L}$ (Grade 1), $< 0.8 \times 10^9/\text{L}$ to $\geq 0.5 \times 10^9/\text{L}$ (Grade 2), $< 0.5 \times 10^9/\text{L}$ to $\geq 0.2 \times 10^9/\text{L}$ (Grade 3), and $< 0.2 \times 10^9/\text{L}$ (Grade 4).
- The above LLNs are defined as:
 - Leukocytes: $\text{LLN} = 4.0 \times 10^9/\text{L}$
 - Neutrophils: $\text{LLN} = 2.0 \times 10^9/\text{L}$
 - Platelets: $\text{LLN} = 150 \times 10^9/\text{L}$
 - Lymphocytes: $\text{LLN} = 1.1 \times 10^9/\text{L}$
- With additional categories:

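### Treatment-emergent high values of four blood counts are not tabulated as incidence in Periods 2 and 3, because the SAP analysis that replaces them looks only at low values

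*SAP*

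**What the plan says.** Protocol 9.5.2 commits to reporting the "incidence of treatment-emergent abnormal, high, or low laboratory values" and defines both directions for continuous tests. It exempts no analyte.

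SAP 6.12.4 turns this into a table: patients with "treatment-emergent or follow-up emergent abnormal, high, or low for laboratory tests will be summarized by treatment group for each study period", meaning Periods 2, 3 and 4. Unscheduled and repeat samples count, and Period 2 is compared by Fisher's exact test.

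The SAP then takes out the liver tests (ALT, AST, total bilirubin, ALP) and four blood counts: "neutrophils, leukocytes, platelets, and lymphocytes will not be included in the treatment-emergent abnormal, high, or low summary". The reason given for the counts is that "a separate analysis addressing leukocytes (WBC) and platelets is described in Section 6.12.4.1". The preceding bullet nevertheless sets a lower limit for the same counts, "where Lilly defined LLN will be used for these 4 labs", and gives no separate upper limit for them.

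SAP 6.12.4.1 is a shift table that counts those "shifting from baseline to a minimum postbaseline result in each relevant category by treatment groups for study Period 2, Period 3"; a pooled version of the two periods is planned as well. Its rule for the postbaseline side is "Use the minimum nonmissing postbaseline value within each study period", and the baseline side is also a minimum. The categories are normal (at or above the LLN) and Grades 1 to 4 below it. The accompanying box plot is minimum to minimum as well.

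**The concern.** The exclusion is justified by a cross-reference, so the section referred to should supply what is removed. The removed table counts patients with new high values and patients with new low values. The replacement appears to address only the second. If so, a protocol-specified safety summary disappears for four counts without a stated reason, and nobody reading the tables could say how many patients per arm went above the normal range on treatment. Infections and cytopenias are both adverse events of special interest in Protocol 8.2.2, so these counts belong to the routine safety picture. The same sentence also raises the question of what is tabulated for them in Period 4, where Appendix 2 of the protocol schedules hematology at Visits 801 and 802.

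**Working it through.** The plan gives no event count here, so there is no figure to reproduce. The check is of the category rule, then of the other outputs, then of Period 4.

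**1. Can SAP 6.12.4.1 register a high value?** Inputs are its LLNs and grade cut-points (x10^9/L). Rule: take the patient's minimum; it is normal if it is at or above the LLN, otherwise it is graded. The test value of 10 x LLN is an arbitrary extreme, not a figure from the documents.

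| Count | LLN | Cut-points below LLN | 10 x LLN | Category |
|---|---|---|---|---|
| Leukocytes | 4.0 | 3.0, 2.0, 1.0 | 40 | Normal |
| Neutrophils | 2.0 | 1.5, 1.0, 0.5 | 20 | Normal |
| Platelets | 150 | 75, 50, 25 | 1500 | Normal |
| Lymphocytes | 1.1 | 0.8, 0.5, 0.2 | 11 | Normal |

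The table covers a patient whose every postbaseline value is ten times the LLN. A single peak fares no better. With postbaseline values of 1.2, 10 and 1.3 times the LLN, the minimum is 1.2 x LLN (leukocytes: 4.8, 40 and 5.2, minimum 4.8), which is normal. So 0 of 4 counts can yield a high result. The extra row for increases compares categories of minima and cannot flag one either. Low values in Periods 2 and 3 are covered, because a shift from normal to any grade is visible.

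**2. Do other outputs in Periods 2 and 3 give the incidence of highs?**

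- The full by-patient listing in SAP 6.12.4 contains every value, but gives no count by arm.
- The listing of abnormal results for these counts uses the shift-table criteria without the normal category, so a high value is filtered out as normal.
- The box plots show a maximum at each visit and reference lines, but not how many patients exceed the limit. They and the change-to-last-observation summaries omit unscheduled and repeat samples, which the removed table would have used.
- The infection listing in SAP Table RHBW.6.8 attaches only the Period 2 minimum of these counts.

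None of these supplies a by-arm patient count. Missing: 4 counts x 2 periods = 8 analyte-period summaries of highs.

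**3. What happens in Period 4?** SAP 6.12.4 plans "treatment-emergent or follow-up emergent abnormal, high, or low for laboratory tests" and defines the two kinds of result separately. The exclusion sentence names only the treatment-emergent one.

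- Read literally, the four counts stay in the follow-up emergent table. Highs would then be counted in follow-up but not on treatment.
- Read broadly, they are gone from Period 4 too. The shift table does not extend to that period. SAP 6.12.4.2 covers only neutrophil recovery in patients who entered below 1500 cells/uL and below their own baseline, and SAP 6.12.3.1 generally drops special-interest summaries in Period 4 except hepatic laboratory tests. A new low in follow-up would have no laboratory table.

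**4. Is the narrowing deliberate?** The text does not say so. The liver tests removed in the same sentence have a replacement built on maxima, the direction in which they are examined, and their combined ALT and bilirubin criterion extends to Period 4. Monocytes, eosinophils and basophils are also named in 6.12.4.1 but are not excluded, so high basophils would be counted and high neutrophils would not.

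**The case against.** The strongest reply is that low counts are what this protocol worries about. The special-interest category is cytopenias, the discontinuation thresholds for these counts are all low, and neutropenia monitoring looks only downward. No passage names a high count as a safety signal. The liver replacement is also one-directional, and nobody proposes to restore low ALT. Protocol 9.5 leaves details to the SAP, and Protocol 9.2 lets changes short of a principal feature be explained in the study report. Laboratory findings that lead to a diagnosis are reported as adverse events in any case.

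Much of this stands. It limits the weight of the point, and it means no protocol amendment is needed. It does not close the gap: the SAP offers no argument that highs are unimportant, only a cross-reference that does not cover them, and adverse event reporting depends on a diagnosis being made.

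Two stronger readings are tempting and should be resisted. A reader might infer that high values appear in no table or listing at all. That is wrong: the full listing has them, and the box-plot tables show maxima. A reader might also infer that follow-up abnormalities in these counts are never counted. The documents do not support that: the exclusion does not mention the follow-up emergent summary, neutrophil recovery is tabulated, and clinically reported events appear as follow-up emergent adverse events by preferred term.

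**Conclusion.** The point holds for treatment-emergent high values. For neutrophils, leukocytes, platelets and lymphocytes, no planned table gives patient incidence above the upper limit in Period 2 or Period 3, contrary to Protocol 9.5.2. The Period 2 Fisher comparison goes with it. This follows from the category definitions and needs no numerical assumption.

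For Period 4 the conclusion is only that the text is ambiguous. A loss of new lows there would rest on the broad reading of the exclusion.

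The number of patients affected cannot be judged from the documents. Primary and major secondary conclusions are untouched. It is a correction that should be made to a descriptive safety table, using data already collected.

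**What to change.** In SAP 6.12.4, keep the four counts in the treatment-emergent summary for Periods 2 and 3, at least for high values. State that the upper limit is the performing laboratory's, that scheduled, unscheduled and repeat measurements all count, and that Period 2 is compared by Fisher's exact test. The 6.12.4.1 shift table can continue to serve for low values in those periods.

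Add that the four counts remain in the Period 4 follow-up emergent high/low summary, with the sponsor-defined LLN for lows. If that is stated, a Period 4 shift table is not needed.

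The cost is a sentence or two in the SAP and a few extra descriptive rows. No new data are required and no other analysis changes.
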